1.3. Secondary Objectives

- Determine response rates and duration of response, early tumor size changes, the toxicity, and overall survival in patients with DTC treated with cediranib or cediranib plus lenalidomide.
- Determine whether the presence of *B-RAF* or *K-RAS* mutations in patients with DTC predict response to cediranib or cediranib plus lenalidomide.

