3. PATIENT SELECTION

3.1. Eligibility Criteria

- 3.1.1. Patients must have histologically or cytologically confirmed papillary, follicular, papillary/follicular variant or Hürthle cell carcinoma. Patients must be felt to be poor candidates for or refractory to further surgery or radioactive I-131 therapy. I-131 therapy must have been completed at least 4 weeks prior to enrollment. All patients are expected to be on thyroxine suppression therapy.
- 3.1.2. Patients must have radiographically measurable disease. Radiographically measurable disease is defined as at least one lesion that can be accurately measured in at least one dimension (longest diameter to be recorded) as >20 mm with conventional techniques or as >10 mm with spiral CT scan. Lesions in previously irradiated anatomic areas (external beam radiation) cannot be considered target lesions unless there has been documented growth of those lesions after radiotherapy.
- 3.1.3. Patients must have evidence of disease progression (20% objective growth of existing tumors by RECIST criteria) within the last 12 months.
- 3.1.4. In the Phase I portion, there is no limit on prior systemic therapies (cytotoxic or targeted therapies). However, patients who have discontinued previous VEGF inhibitors secondary to adverse events are not eligible. In the Phase 2 portion,

patients cannot have received more than 1 prior chemotherapy (cytotoxic or targeted) regimen. Prior VEGF-pathway inhibitors or B-RAF inhibitors are permissible.

3.1.5. Although there are data for lenalidomide in pediatric populations,²³ no dosing or adverse event data is currently available on the use of cediranib or cediranib with lenalidomide in patients <18 years of age. Therefore, children are excluded from this study but will be eligible for future pediatric phase II combination trials.

3.1.6. Life expectancy of greater than 12 weeks.

3.1.7. ECOG performance status 0-2 (Karnofsky >60%; see Appendix A).

3.1.8. Patients must have normal organ and marrow function as defined below:

X leukocytes	>3,000/mcL
X absolute neutrophil count	>1,500/mcL
X platelets	>100,000/mcL
X hemoglobin	>9 g/dL
X serum calcium	<12.0 mg/dL
X total serum bilirubin	below or equal to upper limit of institutional normal**
X AST(SGOT)/ALT(SGPT)	≤2.5 X institutional upper limit of normal
X creatinine	below or equal to upper limits of institutional limits

OR

X creatinine clearance	>50 mL/min/1.73 m ² for patients with creatinine levels above institutional normal

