9.1. Rationale

Archival tumor tissue:

B-RAF gene

K-RAS gene

Pharmacogenomics:

Advanced thyroid carcinoma is a heterogeneous group of diseases likely caused by a variety of molecular defects. Variable responses in previous clinical trials are likely due in part to differences in the underlying disease processes. Data from studies with other targeted agents suggest that different molecular aberrations may affect clinical response. For example, in the Phase II clinical trial with motesanib diphosphate with advanced DTC, DNA from 33 tumors of trial patients was screened for mutations often observed in DTC. Six of the 10 patients (60%) whose tumor contained the *B-RAF*^{V600E} mutation had either a partial response or durable stable disease. In contrast 5 of 15 patients without the mutation (33%) had a partial response or durable stable disease.²⁵ While the number of tumor samples was too small to show significance, the findings do suggest that *B-RAF* mutations may affect response. In addition, in a Phase II study of the multi-target tyrosine kinase inhibitor sorafenib, of sixteen DTC patients who had genotype testing, those with *B-RAF*^{V600E} mutations had significantly longer PFS compared to those who did not (84+ weeks versus weeks).²⁶ *B-RAF* mutations have been reported in 29-83% of PTCs and *K-RAS* mutations have been found in 21-50% of FTCs.²⁷ We plan to evaluate *B-RAF* mutations and *K-RAS* mutations in available tumor samples to assess whether these mutations predict response. This study will provide an excellent opportunity to further clarify the role of the previously described polymorphisms in thyroid carcinoma.

Shipping Instructions:

The shipment of all human samples (tissue) must comply with appropriate regulations as specified by the carrier. Paraffin archival tissue can be shipped at room temperature. The outer container must be puncture resistant (e.g., cardboard mail tube, corrugated cardboard box). A biohazard sticker must be affixed to both the inner and outer containers.

All shipments must contain a completed Sample Identification form (Appendix F).

Archival Tumour Samples can be shipped to the address below Monday through Thursday.

Shipping address:

University of Chicago
HTRC, Room P-616
[name]
Chicago, IL 60637
[contact]
E-mail: [contact]

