13. STATISTICAL CONSIDERATIONS

13.1. Study Design/Endpoints

13.1.1. Phase I.

The phase I trial will use a 3+3 design with the MTD defined as the highest dose level such that <2 of 6 patients experience dose-limiting toxicity.

13.1.2. Phase II.

There is no standard therapy for differentiated thyroid cancer that is refractory to radioactive iodine. The best studied agent in this disease, doxorubicin, has an estimated response rate of 10%. Although cediranib has not been studied in thyroid cancer, a phase II study of the VEGF inhibitor motesanib diphosphate showed a median progression-free survival (PFS) of 40 weeks. Because we hypothesize that combination therapy will be more effective than single agent treatment, we will randomize in a 1:2 ratio, which should enhance recruitment. The randomization will be stratified by prior therapy with a VEGF-pathway inhibitor (yes vs. no) and performance status (0-1 vs. 2)

The primary endpoint will be PFS, which will be compared between the two treatment arms using a stratified logrank test. To determine the sample size, we noted that the median PFS in 93 patients with radioiodine-resistant thyroid cancer treated with motesanib diphosphate²⁵ was 40 weeks. We therefore assume a median of 40 weeks for the cediranib alone arm. In order to have 85% power to detect a 75% improvement in the median to 70 weeks with combination therapy (hazard ratio [HR]=1.75), 110 patients will be required (36 randomized to cediranib and 74 to cediranib plus lenalidomide), based on a one-sided test at the $\alpha=0.10$ significance level. This calculation assumes 1 year of accrual (9 patients per month) and 1.5 years of additional follow-up for a total study duration of 2.5 years. Kaplan-Meier³⁰ curves will be generated for each treatment arm and the median PFS times estimated using the Brookmeyer and Crowley method³¹. In addition to the logrank test, PFS in the two groups will be analyzed by fitting a Cox³² proportional hazards regression model, adjusting for prior VEGF inhibitor use, performance status, and other baseline risk factors. The goodness of fit of the Cox model and the appropriate functional form for continuous covariates will be assessed using graphical techniques, including inspection of martingale residual plots.

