13.3. Stratification Factors

Phase II. Patients will be stratified on prior use of VEGF-pathway inhibitors (yes vs no) and performance status (0 and 1 vs 2).

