13.4. Analysis of Secondary Endpoints

13.4.1. Phase I.

The objective response rate of cediranib in combination with lenalidomide in patients with iodine refractory, unresectable DTC who have evidence of disease progression within 6 months of study enrollment will be estimated. In addition, the toxicity, duration of response, progression free survival, and overall survival in patients with DTC treated with cediranib plus lenalidomide will be evaluated.

13.4.2. Phase II.

Overall survival (OS) rates will be estimated and compared between groups using methods similar to that described above for PFS. Response rates will be compared using a chisquare test followed by logistic regression analysis to adjust for covariates.

The percent change in tumor size from baseline to the end of cycle 2 (two months) will be compared between the two groups using a two-sample t test³³. The post-treatment total sum of lengths for a patient with a new lesion will be scored as $1.2 * \max(\text{pre-sum}, \text{post-sum})$ to ensure that the appearance of new lesions corresponds to a disease progression per RECIST criteria. In the event of any early deaths prior to two months, a nonparametric rank sum test will be used in place of the t test, with deaths ranked at the extreme end of the distribution.

Adverse events will be summarized by type and grade. Adverse event rates will be compared between the two treatment groups using a chisquare test for common toxicities and Fisher's exact test for less frequent events.

Repeated measures analysis of variance (RM ANOVA) will be performed to determine the effect of the treatments on serial measurements of TSH and thyroglobulin. It is hypothesized that these levels will decrease over time. Baseline tissue biomarker expression, scored as present or absent, of *B-RAF* and *RAS* mutations will be correlated with response rates using Fisher's exact test, and with PFS and OS by fitting a Cox proportional hazards regression model.

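### The B-RAF/RAS analysis of response is a crude Fisher test that takes no account of histology and does not report by regimen

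*Combined protocol and SAP*

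**What the plan says.** Section 1.3 asks whether B-RAF or K-RAS "mutations in patients with DTC predict response to cediranib or cediranib plus lenalidomide". Section 13.4.2 gives the only analysis. Mutation status, scored present or absent, "will be correlated with response rates using Fisher's exact test", "and with PFS and OS by fitting a Cox proportional hazards regression model". It names no arm, histology or other covariate for these analyses.

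Covariates appear elsewhere, but for comparing arms. Section 13.1.2 has a PFS Cox model "adjusting for prior VEGF inhibitor use, performance status, and other baseline risk factors", and Section 13.4.2 follows the chi-square comparison of response between arms with a logistic regression. Randomisation is stratified by prior VEGF-pathway inhibitor and performance status (Section 13.3), not histology.

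Section 3.1.1 admits "confirmed papillary, follicular, papillary/follicular variant or Hürthle cell carcinoma". Section 9.1 reports B-RAF mutations in 29-83% of papillary cancers and says that K-RAS "mutations have been found in 21-50% of FTCs". Section 2.4.1 makes the same links and adds that B-RAF has been associated with more aggressive, iodine-resistant disease. It also says that tissue is analysed only where archival material exists.

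The gene is named inconsistently. Section 1.3 says K-RAS, Section 9.2 describes a K-RAS codon 12/13 assay, and Section 13.4.2 says RAS.

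**The concern.** Mutation status is not randomised. On the protocol's own account it travels with tumour type, so carriers and non-carriers will differ in histology. A 2x2 Fisher test of mutation by response has no place for a third variable. If papillary and follicular tumours respond at different rates for reasons unrelated to the mutation, the test attributes that difference to the mutation. The plan thus allows covariates in the randomised comparison, where confounding is not expected, and names none in the comparison where it is.

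The objective also names cediranib and cediranib plus lenalidomide separately, while the analysis text does not say that results will be shown for each. At stake is the interpretation of one secondary objective.

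**Working it through.** **The plan's own figures.** None is given for the mutation analysis. The primary design supplies the event count used in step 4. The Schoenfeld formula, with HR 1.75, one-sided alpha 0.10, power 85% and a 36/110 share in the smaller arm, gives (1.2816 + 1.0364)² / [0.327 × 0.673 × (ln 1.75)²] = 78 events. Section 13.1.2 projects 80, so the figure is reproduced.

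**1. Formula for the histology effect.** Let w be the papillary share, p the B-RAF prevalence in papillary tumours (zero elsewhere), and r_P and r_F the response rates in papillary and other tumours. Mutation has no effect within histology.

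- Response in carriers = r_P.
- Response in non-carriers = [w(1−p)r_P + (1−w)r_F] / [w(1−p) + (1−w)].
- False difference = (r_P − r_F) × (1−w) / [w(1−p) + (1−w)].

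The range p = 0.29 to 0.83 is from Section 9.1. The value w = 0.70 is an assumption, at the low end of the 70-80% that Section 2.1 gives for thyroid cancer overall. The values of r_P and r_F, and the absence of B-RAF outside papillary tumours, are also assumptions.

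**2. Results at w = 0.70.** The multiplier is 0.30/0.797 = 0.376 at p = 0.29 and 0.30/0.419 = 0.716 at p = 0.83.

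| Assumed response, papillary vs other | p = 0.29 | p = 0.83 |
|---|---|---|
| 40% vs 20% | 7.5 points | 14.3 points |
| 30% vs 20% | 3.8 points | 7.2 points |
| no gap | 0 | 0 |

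A lower papillary share raises these figures. The thalidomide trial described in Section 2.1 had 13 papillary (including tall cell) among 29 non-medullary patients, about 45%. At w = 0.45 the multipliers are 0.55/0.8695 = 0.633 and 0.55/0.6265 = 0.878. The 30% vs 20% range becomes 6.3-8.8 points and the 40% vs 20% range 12.7-17.6 points.

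**3. Effect on the test.** I enumerated the rejection probability of Fisher's test (two-sided 0.05) at w = 0.70 with no mutation effect.

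| Assumed response | Tissue from all 110 | Tissue from half |
|---|---|---|
| 40% vs 20% | 9-31% | 5-17% |
| 30% vs 20% | 5-10% | 4-6% |

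With no gap the test stays below 5%. The inflation is therefore material only if the histology gap is fairly large and tissue is widely available.

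**4. What an interaction analysis could show.** For PFS, the standard error of the log ratio of hazard ratios is 1/√[E × a(1−a) × m(1−m)], where a = 36/110 and m is the mutation prevalence. Prevalence of 30-50% and tissue from half or all patients are assumptions.

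| Events with tissue (E) | SE (m = 0.5 to 0.3) | Power for ratio 2.0, two-sided 0.05 | Ratio detectable with 80% power |
|---|---|---|---|
| 80 | 0.477-0.520 | 31-27% | 3.8-4.3 |
| 40 | 0.674-0.735 | 18-15% | 6.6-7.9 |

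**5. Why results are needed by arm.** Suppose carriers respond at 10% on cediranib and 40% on the combination, and non-carriers at 30% on both (assumed rates). With carriers split between arms as 36:74, pooled response in carriers is (36 × 0.10 + 74 × 0.40)/110 = 30.2%, against 30.0% in non-carriers. An analysis that combines the arms would see nothing.

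**The case against.** The strongest defence is that the plan answers the question the protocol asks. Section 9.1 uses prediction of response in a loose sense. Its example is response or durable stable disease in 6 of 10 mutated and 5 of 15 unmutated tumours, all treated with motesanib. That is association among treated patients, with no comparison of treatments. A reader might infer that the analysis cannot answer the objective at all because it lacks an interaction term. The documents do not support that: in the sense of Section 9.1, Fisher's test does answer it, though crudely.

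Three other stronger readings also fail.

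- A reader might take the Cox text to exclude arm and covariates. It is silent on them, so for PFS and OS this is under-specification.
- A reader might think that leaving out arm biases the mutation comparison. Arm is randomised, so omitting it loses regimen-specific information but does not itself confound.
- A reader might expect an interaction model to sort prognosis from prediction. Both arms receive cediranib, so the mutation effect within an arm mixes the two. The interaction speaks only to adding lenalidomide.

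The defence can also say that the bias is hypothetical. The 40% vs 20% case implies 34% response overall (0.7 × 40% + 0.3 × 20%), above the partial response rates quoted in Section 2.1: axitinib 30%, motesanib 14%, lenalidomide 22%, thalidomide 5 of 28. The smaller gap is easier to credit, and no gap gives no bias. Finally, a model with arm, interaction, histology and both stratification factors is too large for this tissue set. With tissue from half of the 36 patients on cediranib alone and 30-50% prevalence, that arm has about 5-9 carriers.

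These limits stand. What remains is that the named method for response cannot account for a confounder the protocol itself describes, or show the two regimens separately unless it is run within each arm.

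**Conclusion.** The point holds as a cheap improvement to a secondary analysis. For response, the specified test leaves mutation and histology entangled, and the plan does not promise results by regimen. At 70% papillary, with B-RAF confined to papillary tumours at 29-83% and no true mutation effect, the false difference is 3.8-7.2 points if response is 30% vs 20% and 7.5-14.3 points if it is 40% vs 20%. It is zero if histologies respond alike. The documents do not say which of these applies, so no particular bias is established. For PFS and OS the defect is missing detail. The primary comparison of arms is unaffected.

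**What to change.** In Section 13.4.2:

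- Replace the crude Fisher test with a histology-stratified exact test, or a Firth logistic model with histology. Where a mutation is confined to one histology, this amounts to a comparison within that histology, and the report should say so.
- Report mutation effects on response with confidence intervals separately in each arm.
- Include histology and arm in the PFS and OS Cox models, with few other terms.
- Give the arm-by-mutation interaction as exploratory only.
- State that, because both arms receive cediranib, the interaction addresses only the addition of lenalidomide, and that a mutation effect within an arm is an association that cannot separate prognosis from prediction of cediranib benefit.
- Name K-RAS codons 12/13 in place of RAS, to match Sections 1.3 and 9.2.

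The cost is analysis text. Histology is established for eligibility (Section 3.1.1) and diagnosis is recorded at registration (Section 4.2), so no new data are needed. The downside is wide intervals and low interaction power: about 15-31% for a ratio of hazard ratios of 2.0, under the assumed prevalence and tissue availability.

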13.5. Reporting and Exclusions

13.5.1. **Evaluation of toxicity.** All patients (Phase I and II) will be evaluable for toxicity from the time of their first treatment with cediranib or cediranib plus lenalidomide.

13.5.2. **Evaluation of response.** All patients included in the study (Phase I and II) will be assessed for response to treatment, even if there are major protocol treatment deviations or if they are ineligible. Each patient will be assigned one of the following categories: 1) complete response, 2) partial response, 3) stable disease, 4) progressive disease, 5) early

death from malignant disease, 6) early death from toxicity, 7) early death because of other cause, or 9) unknown (not assessable, insufficient data).

All of the patients who met the eligibility criteria (with the possible exception of those who received no study medication) will be included in the main analysis of the response rate. Patients in response categories 4-9 will be considered to have a treatment failure (disease progression). Thus, an incorrect treatment schedule or drug administration will not result in exclusion from the analysis of the response rate.

All conclusions will be based on all eligible patients. Subanalyses may then be performed on the basis of a subset of patients, excluding those for whom major protocol deviations have been identified (e.g., early death due to other reasons, early discontinuation of treatment, major protocol violations, etc.). However, these subanalyses will not serve as the basis for drawing conclusions concerning treatment efficacy, and the reasons for excluding patients from the analysis will be clearly reported. Data will be reported to CTEP using CDUS -Complete.

REFERENCES

1. National Cancer Institute. Surveillance, Epidemiology, and End Results (SEER) Program. <http://seer.cancer.gov/> Accessed 2009.
2. American Cancer Society. www.cancer.org/docroot/home/. Accessed 2009.

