Thalidomide was originally developed as a sedative in the 1950s, but its teratogenic effects led to its discontinued usage in that setting. Thalidomide, however, was noted to have anti-angiogenic effects. It has been shown to be an effective therapy for multiple myeloma; in addition, it is currently under evaluation for treatment of a variety of other cancers although its exact mechanism remains uncertain. Because thalidomide is not activated in rodent models, preclinical efficacy studies have not been useful. Ain and colleagues assessed thalidomide's effectiveness in patients with progressive thyroid cancer in a Phase II trial.⁹ A total of 36 patients (11 PTC, 2 tall cell PTC, 4 FTC, 8 HCC, 4 insular, 7 MTC) with radioiodine-unresponsive progressive disease were recruited. Daily oral thalidomide was administered at a starting dose of 200 mg and increased over 6 weeks to 800 mg or to the maximum tolerated dose. Of 28 patients available for evaluation, 5 had partial responses with a median duration of 4 months and 9 had stable disease for a median duration of 6 months. Fatigue was the most commonly reported side effect. Serious adverse events included infection, pericardial effusion, and pulmonary embolus. A Phase II study with lenalidomide, a derivative of thalidomide with less toxicity, also showed anti-cancer activity. Data from a Phase II study of lenalidomide in patients with progressive iodine-refractory thyroid cancer has been presented.¹⁰ A total of 25 patients were initiated on 25 mg of oral lenalidomide daily. Of 18 evaluable patients, 67% were responders (22% with partial response and 44% with stable disease.) Grade 3 toxicities, neutropenia and thrombocytopenia responded to dose reduction. The mean daily dose was 20 mg.

Patient Population:

Patients with iodine refractory DTC have few therapeutic options. Cytotoxic chemotherapy is often ineffective and the most studied agent, doxorubicin, is associated with significant toxicity.

Study Design:

This is a phase I study followed by a phase II, 2 arm, open-label, randomized trial of cediranib alone or in combination with lenalidomide.

Patients should have measurable disease (papillary, follicular, Hürthle cell type, or other

papillary/follicular variants) and evidence of disease progression (objective growth of existing tumors within the last 12 months).

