------------------------	---

** Patients with hyperbilirubinemia due to Gilbert's syndrome may enroll in the trial.

3.1.9. Patients must have QTc < 480 msec.

3.1.10. The following groups of patients are eligible provided they have New York Heart Association Class II (NYHA; see Appendix G) cardiac function on baseline ECHO/MUGA:

- * those with a history of Class II heart failure who are asymptomatic on treatment
- * those with prior anthracycline exposure
- * those who have received central thoracic radiation that included the heart in the radiotherapy port.

3.1.11. Females of childbearing potential (FCBP)[†] must have a negative serum or urine pregnancy test with a sensitivity of at least 25 mIU/mL within 10 – 14 days prior to and again within 24 hours of starting lenalidomide and must either commit to continued abstinence from heterosexual intercourse or begin TWO acceptable methods of birth control, one highly effective method and one additional effective method AT THE SAME TIME, at least 28 days before she starts taking lenalidomide. FCBP must also agree to ongoing pregnancy testing. Men must agree to use a latex condom during sexual contact with a FCBP even if they have had a successful vasectomy. All patients must be counseled at a minimum of every 28 days about pregnancy precautions and risks of fetal exposure. See Appendix H: Risks of Fetal Exposure, Pregnancy Testing Guidelines and Acceptable Birth Control Methods, AND also Appendix I: Education and Counseling Guidance Document.

[†] A female of childbearing potential is a sexually mature woman who: 1) has not undergone a hysterectomy or bilateral oophorectomy; or 2) has not been naturally postmenopausal for at least 24 consecutive months (i.e., has had menses at any time in the preceding 24 consecutive months).

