4.2. Registration Process

All patients must be registered with the University of Chicago Registrar at least 48 hours prior to the commencement of treatment. The following documents should be completed by the research nurse or data manager and faxed [contact] or emailed [contact] to the Registrar:

- Provider of information
- Treating Physician
- Patient name and hospital ID number
- Patient's zip code of residence
- Date & copy of signed informed consent
- Race, gender, date of birth of patient
- Diagnosis and date of initial diagnosis
- Prior therapy with a VEGF-pathway inhibitor (yes/no)
- ECOG performance status
- Complete **Phase II Consortium Affiliate Clinical Trial Patient Registration Form**
- Source documentation for eligibility and pre-study procedures

The research nurse or data manager at the participating site will then call [contact]) or e-mail [contact] to confirm all selection criteria listed in Section 4.0. To complete the registration process, the Coordinator will:

- Assign a patient study number
- Register the patient on the study
- Fax or e-mail the patient study number and dose to the participating site

Call the research nurse or data manager at the participating site and verbally confirm registration.

Each site must have two trained counselors available for counseling all patients receiving lenalidomide supplied by the Division of Cancer Treatment and Diagnosis. Trained counselors must complete training using the online program provided free by Celgene, the Lenalidomide Counseling Program (LCP). Registration for LCP is done by completing the form found in Appendix K and following the directions provided in the email notification. After the training is complete, the counselors must generate a training certificate and provide it to the PMB for documentation. Sites may not order lenalidomide until documentation for two trained counselors is provided to the appropriate office.

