5.1.2. Cediranib and lenalidomide administration

Please note, as of **April 10, 2015**, patients assigned to Arm B (Combination of cediranib and lenalidomide) are to discontinue lenalidomide and may continue on cediranib alone.

After determining the MTD or reaching the maximum dose specified above of cediranib with lenalidomide in the Phase I portion of this study, the Phase II study will be initiated.

Subjects will be randomized in a 1:2 ratio to one of two arms. Randomized stratification will employ prior therapy with a VEGF-pathway inhibitor (yes vs. no) and performance status (0 and 1 vs. 2). In Cohort A, subjects (n = 36) will receive cediranib alone at 30 mg daily. In Cohort B, subjects (n = 74) will receive cediranib and lenalidomide at the dose determined in the Phase I study. Each cycle will be 4 weeks in length. Disease re-evaluation will occur every 8 weeks using RECIST guidelines. After 18 cycles, disease re-evaluation will occur every 16 weeks. Patients without evidence of anti-thyroglobulin antibodies will continue to have thyroglobulin levels measured at each response assessment (usually every 8 weeks). All patients are expected to be on thyroxine suppression therapy and thyroid stimulation hormone (TSH) levels will be monitored pre-therapy and every 8 weeks during therapy.

- Patients will take cediranib or cediranib and lenalidomide. Cediranib will be taken daily at 30 mg. Lenalidomide will be taken on day 1-21 of the 28 day cycle at 15 mg. Proper administration of cediranib and lenalidomide is described in Section 5.1. A 4-week period constitutes one cycle of treatment.
- Patients will be provided with a Medication Diary for cediranib and lenalidomide (Appendix B), instructed in its use, and asked to bring the diary with them to each

appointment. A new copy of the Medication Diary will be given to patients each cycle and for those whose dose is reduced due to adverse events.

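### Section 13.5.2 bases the Phase II response analysis, and on its plain reading PFS and OS, on eligible rather than all randomised patients

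*Combined protocol and SAP*

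**What the plan says.** Phase II is a "phase II, 2 arm, open-label, randomized trial of cediranib alone or in combination with lenalidomide" (section 2.1), and section 5.1.2 states "Subjects will be randomized in a 1:2 ratio to one of two arms". The size is set in section 13.1.2 by numbers randomised: "110 patients will be required (36 randomized to cediranib and 74 to cediranib plus lenalidomide". That section compares PFS by a stratified logrank test but names no analysis population.

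The only text on who enters an efficacy analysis is section 13.5.2, which serves Phase I and Phase II together. It says three things in turn:

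- Every patient "will be assessed for response to treatment, even if there are major protocol treatment deviations or if they are ineligible".
- For the main response-rate analysis, "All of the patients who met the eligibility criteria (with the possible exception of those who received no study medication) will be included".
- "All conclusions will be based on all eligible patients".

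The same paragraph allows further analyses that leave out patients with major deviations, but says these cannot support conclusions about efficacy. No intention-to-treat or all-randomised set is defined. No section says who may rule a patient ineligible after randomisation, by when, or without knowledge of arm and outcome.

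**The concern.** An eligible-only rule suits a single-arm response estimate. In a randomised comparison it allows patients to be removed after allocation, and randomisation no longer protects the comparison against the reasons for removal. Here the arm is known to site and investigator, and response and progression are assessed at the site. An ineligibility ruling could therefore be made with both arm and outcome in view.

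Some entry criteria leave room for a later change of view. Section 3.1.3 asks for 20% growth by RECIST within the past 12 months. Section 3.1.2 lets an irradiated lesion count as a target if it has grown since radiotherapy, while section 11.1.2 treats lesions in irradiated areas as not measurable. Whether a patient with only such a lesion is eligible depends on which section is applied.

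Two things are at stake: power, because all 110 randomised patients are needed for the stated figure; and type I error, if rulings are related to both outcome and arm.

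**Working it through.** **Inputs (section 13.1.2 and the futility paragraph that follows it).** 36 and 74 patients; medians 40 and 70 weeks (HR 1.75); one-sided α = 0.10; power 85%; accrual 1 year; further follow-up 1.5 years; 80 projected events. The ineligibility rate is not given, so the rates below are assumptions.

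**1. Reproduce the plan's figure.** Schoenfeld: d = (z₁₋α + z₁₋β)² / [p(1−p)(ln HR)²], with p = 36/110 = 0.3273.

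- p(1−p) = 0.2202; (ln 1.75)² = 0.5596² = 0.3132.
- d = (1.2816 + 1.0364)² / (0.2202 × 0.3132) = 5.373 / 0.06895 = 77.9, so 78 events against 80 stated.
- Power = Φ(√[d·p(1−p)] · ln HR − 1.2816). With d = 80 this is Φ(1.067) = 85.7%.
- Expected events with exponential PFS and uniform accrual: the event probability is 1 − [e^(−λF) − e^(−λ(A+F))]/(λA), with A = 52.18 and F = 78.27 weeks. This gives 0.830 (median 40) and 0.640 (median 70), so 36 × 0.830 + 74 × 0.640 ≈ 77.3 events and power Φ(1.027) = 84.8%.

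The plan's numbers are sound when all 110 patients are analysed.

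**2. Balanced exclusion, unrelated to arm or prognosis.** Events shrink in proportion.

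| Excluded | N analysed | Events (from 77.3) | Power | Power from 80 events |
|---|---|---|---|---|
| 0% | 110 | 77.3 | 84.8% | 85.7% |
| 5% | 104.5 | 73.4 | 83.4% | 84.3% |
| 10% | 99 | 69.5 | 81.8% | 82.8% |

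The cost is 1.4 points at 5% and 3.0 at 10% (from 80 events, 1.4 and 2.9). In 4,000 simulated null trials with 10% removed from both arms at random, one-sided error was 10.8% with and without removal.

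**3. Outcome-related exclusion from one arm only.** Under no effect with a 40-week median, the chance of progression by week 16 is 1 − 2^(−16/40) = 0.242, or 74 × 0.242 = 17.9 patients in Arm B. Ruling 10% or 20% of them ineligible removes 1.8 or 3.6 patients. Two separate simulations used the plan's scan schedule and a week-130 cut-off:

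| Arm B early progressors removed | 3,000 trials | 4,000 trials |
|---|---|---|
| none | 10.1% | 10.4% |
| 10% (about 2 patients) | 12.0% | 12.6% |
| 20% (about 4 patients) | 16.0% | 15.2% |

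Simulation standard errors are √[0.1 × 0.9/3000] ≈ 0.5 points at the 10% level and slightly more at 16%, so the two sets agree.

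**4. Direction.** In a further simulation, 10% of each arm was ineligible, with twice the hazard of the rest. Removing them from Arm A only took one-sided error from 10.5% to about 6%. Removing them from Arm B only (about 7 patients) took it to about 16%. The sign of the bias depends on which arm loses the patients.

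**The case against.** The strongest objection is scope. The sentence stands under a heading about response, straight after the response-rate analysis, and section 13.1.2 sizes and describes the PFS comparison by randomised arms. A reader might infer that the plan expressly excludes ineligible patients from the PFS test. It does not, because no sentence says so. The reach to PFS and OS comes from the breadth of the sentence, the reference to treatment efficacy in the same paragraph, and the lack of any other population. If the narrow reading is right, the between-arm response comparison in section 13.4.2 is still eligible-only and the primary endpoint has no stated population.

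A reader might also infer that the entry timetable itself produces treated, ineligible patients. Section 4.2 says "All patients must be registered with the University of Chicago Registrar at least 48 hours prior to the commencement of treatment", while section 3.1.11 requires a pregnancy test "again within 24 hours of starting lenalidomide". The documents do not support that inference. Section 8.1.2 and Appendix H withhold study drug until both tests are verified negative, so a late positive test yields a never-dosed patient. Section 3.1.12 applies the same testing to cediranib alone.

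Nor do the documents show that early progressors would be singled out for re-examination. Eligibility source documents reach the registrar before treatment (section 4.2), so late rulings may be few. Appendix E describes audits of selected records and says nothing of re-judging eligibility. The case rests on the absence of a safeguard, not on evidence of misuse.

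Section 13.5.2 does have protections: ineligible patients still receive a response category, unassessable patients count as failures, wrong dosing does not exclude anyone, and reasons for exclusion from the subanalyses must be reported. An all-randomised response analysis therefore remains possible. The effect on response itself is also small. If 3.6 non-responders left 74 patients and true response were 20% or 30% (assumed), the observed rate would be 14.8/70.4 = 21.0% or 22.2/70.4 = 31.5%. These points limit the size of the problem but do not supply the missing population.

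**Conclusion.** The point holds. Followed as written, section 13.5.2 removes randomised and treated patients later ruled ineligible from the main response comparison and, on its plain reading, from the PFS and OS comparisons. The stated sample size and power are correct only if nobody is removed.

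The likely cost is modest: about 1.4 or 3 points of power if 5% or 10% are excluded evenly, with no change in type I error. The 12–16% error is an illustrative worst case. It assumes exclusions that depend on outcome, fall only on Arm B and number about 2 to 4, so it should not be read as the expected error. The mirror case in Arm A makes the test conservative. The simulations use an unstratified logrank test, exponential PFS and assumed rates.

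This should be changed because so few patients can move the result and the remedy costs no sample size. It does not show that the planned comparison is invalid.

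**What to change.** For Phase II, replace the eligible-only rule in section 13.5.2 with text such as: *PFS, OS and response are compared between arms in all randomised patients as assigned, whether or not later found ineligible. An analysis of eligible patients is supportive only.* The eligible-only rule may stay for Phase I.

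Three other places must agree with this:

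- **Section 11.1.6** counts PFS from start of treatment. For Phase II it should count from randomisation, so that never-dosed patients have a defined time origin.
- **Section 11.1.1** calls a patient evaluable for response only after at least one cycle and a re-evaluation, or on early progression. State that this set does not define the between-arm response comparison.
- **Section 4.1** allows registration to be cancelled if no treatment is given. State that a randomised patient stays in the analysis regardless.

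For the supportive analysis, require that ineligibility rulings rest on pre-randomisation data and are made blind to arm and outcome.

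The sample size stays at 110. The cost is a short amendment touching several sections, follow-up of any never-dosed patients, and slight dilution of the effect from a few ineligible or never-dosed patients.
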